7.6 Supportive Analyses of the Secondary Outcome Measures

7.6.1 Demographic Subgroup Analyses

The secondary (efficacy) outcome results will be presented and tested within each demographic subgroup described in Section 7.3.1 by including interactions with treatment assignment in the model. Summaries will include the odds ratio, confidence interval, and p-value similar to the secondary outcome, including a forest plot. The corresponding SAS code is provided below:

```
proc glimmix data = data method = quad;
  class site week participant;
  model y(event = '1') = trt|subgroup mde week site /
    dist = binary link = logit solution;
  random intercept / subject = participant;
run;
```

where:

- data is a dataset with one row per weekly UDS per participant for the specified primary substance of use,
- y is the binary variable with a value of 1 indicating the UDS for that participant was negative and 0 indicating positive UDS result,
- trt is a binary variable with a value of 1 indicating active rTMS and 0 indicating sham rTMS,
- subgroup is the demographic variable of interest,
- mde is a binary variable with a value of 1 indicating the presence of MDE,
- week is the study week (1 – 8, categorical),
- site is a categorical variable containing which of the sites each participant was enrolled in, and
- participant is the participant ID.

7.6.2 Additional Efficacy Analyses

In preparation to assist in designing future larger trials of efficacy, estimates of the MDE, site and participant effects from the secondary outcome analysis may be explicitly given. For the participant effect, this will likely be an estimate of the variance in the outcome attributed to the within participant correlation. Summaries will be provided similar to the secondary outcome, including a forest plot.

Additional supportive analyses of the secondary (efficacy) outcome will include the following:

1. Examine if treatment effect varies depending on study week. This can be accomplished by introducing an interaction between week and treatment in the proposed model as given in the subgroup analysis SAS code and examining the significance of the joint or Type III test on that interaction. If significant, estimates of treatment effect based on study week can be presented. Summaries will be provided similar to the secondary outcome.
2. Repeat the secondary outcome analysis considering all randomized participants (regardless of primary substance of use designation) for UDS results for the following:
 - a) Negative for all substances (amphetamine, barbiturate, buprenorphine, benzodiazepines, cocaine, ecstasy, fentanyl, marijuana, methadone, methamphetamine, opiates, oxycodone, and phencyclidine)
 - b) Negative for stimulants (amphetamine, cocaine, and methamphetamine)
 - c) Negative for primary substance of use (cocaine or methamphetamine as assessed at randomization)
3. Repeat the secondary outcome analysis in the population of participants who met the threshold of 20 rTMS sessions. Three tests will be performed in the participants' primary substance of use: by primary substance of use cocaine, by primary substance of use methamphetamine, and overall.

7.6.3 Sensitivity Analysis

The following sensitivity analyses of the secondary outcome measure will be performed. The analysis method and summaries will be as defined for the secondary outcome.

1. Defining study week as a strict 7-day period from the day of randomization and excluding UDS that were collected outside the respective 7-day period, despite having been collected within study visit windows. Any UDS collected after Study Day 56 will be excluded. The analysis method and summaries will be as defined for the secondary outcome.
2. Defining time as a continuous measure using Study Day.

7.7 Definition of the Exploratory Outcome Measures

Exploratory outcomes may include, and are not limited to:

- Other feasibility measures:
 - Percent of participants that complete all available questions for at least 75% of daily monitoring surveys (mobile questionnaires: MCQ, MMQ)
 - Expected once per day from Study Day 1 (randomization) to Study Day 112 (Week 16 follow-up visit target date)
 - If multiple surveys are completed, the first is retained for analysis
 - Percent of participants that complete all follow-up visits
- Self-reported cocaine and methamphetamine use (Timeline Follow-Back)
- Cocaine and/or methamphetamine craving (Visual Analogue Craving Scale, VAS, found on both CCA and MCQ/MMQ CRFs)
- Depression/anxiety symptoms (Hospital Anxiety and Depression Scale, HADS)
- Sleep quality (Actigraphy; Pittsburgh Sleep Quality Index, PSQI)
- Quality of life (Health Related Quality of Life, HRQOL-4)

- Impact of personal characteristics (age, handedness) on treatment outcomes
- Cognitive Behavioral Therapy (CBT) participation (Dynamicare dataset)
- Motor threshold changes over the treatment course (TMS; Machine output)

7.8 Analyses of the Exploratory Outcome Measures

The other feasibility measures may be analyzed analogously to the primary (feasibility) outcome. The other exploratory outcomes may be summarized and analyzed as appropriate for the type of outcome, such as fisher exact tests and/or logistic regression models for binary outcomes and non-parametric tests of mean/median differences and other types of longitudinal or cross-sectional regression models for ordinal or continuous outcomes.

7.9 Missing Data Analysis

As defined, the primary (feasibility) outcome will have no missing data. Participants that drop out of treatment early will still be evaluated as to whether they attended at least 20 rTMS sessions.

The secondary (efficacy) outcome is expected to have missing data, specifically UDS results. The proposed analysis model takes into account all available data, and missing data are assumed to be missing at random (a weaker assumption than missing completely at random). That is, missingness is allowed to depend on observed covariates. As such, the prespecified analysis method does not need missing data to be imputed or handled in some special way. That being said, alternative methods of handling missing data may be considered as sensitivity analyses.

The first and second methods for missing data analysis will include: 1) imputing all missing secondary outcome measure UDS as negative, and 2) imputing as positive. If there is at least one UDS per study week for a participant, regardless of the timing within the study week or later visits in the study week with missing UDS collection, the outcome is not considered missing. On the other hand, if there is not a single UDS collected within the study week, then the secondary outcome is considered missing.

The third method for handling missing secondary outcome data involves imputation based on self-report collected via Timeline Followback (TLFB). If the secondary outcome measure is missing, then any self-report use of the primary substance of use (cocaine or methamphetamine as defined at baseline) three days prior to the end of the study week window will result in a positive outcome measure of use. The three days prior to the end of the window represent use prior to attending the last visit of the study week because the secondary outcome measure is the last UDS collected per study week. Use of any type (oral, nasal, smoking, non-IV injection, IV injection, or other, as applicable) will count towards a positive result. Only if a participant is missing all UDS within a given study week, will self-report be used to impute the outcome measure. Study week will be calculated as described in Section 3.2.2. If TLFB is also missing, then the secondary outcome measure will not be imputed. Participants will only be included if there is at least one UDS which contributes to the secondary outcome (whether observed or imputed). For example, a participant who attends their first Study Week 1 visit on the first of the month, does not attend any visits during Study Week 2 and therefore has no UDS collected, and attends during Study Week 3 and completes UDS and TLFB. Then the window for Study Week 2 begins on the 8th and ends on the 14th. TLFB collected for the 11th – 13th will be used to impute Study Week 2 results.

For the fourth method of multiple imputation, separate procedures will be used for intermittent missingness and dropout. The following assumptions are made:

1. For the participants with intermittent missingness, assume missing at random (MAR).

When UDS data reflect intermittent missingness, in which an unobserved outcome was followed by observed outcomes, and the participant remained in the assigned intervention group, the observed outcomes can be used to predict the missing values.

2. For the participants who dropout, assume missing not at random (MNAR).

Participants who dropped out may have had different patterns of substance use after dropout than those who remained in the study. The values for missing UDS after dropout might not retain the trend of prior observations since the participant was no longer exposed to the study environment. In fact, substance use patterns after dropout for a participant in the active rTMS treatment arm may more closely resemble participants in the sham treatment arm than other active rTMS participants.

Separate analyses will be performed for CUD and MUD as described for the main analysis of the secondary outcome measure in Section 7.4.

In the first step of imputation, a Markov Chain Monte Carlo (MCMC) method will be used to impute the values of missing outcomes from intermittent missingness under the assumption of MAR. The SAS code for imputing missing data from intermittent missingness is given below. Note the categorical variables (e.g., site, strata) must be in the dataset as dummy variables for MCMC imputation.

```
proc mi data = secondout_wide out = imp1
    minimum = 0 maximum = 1 round = 1
    n impute = 50 seed = 123;
    by trt;
    mcmc impute = monotone chains = multiple;
    var site1 site2 site3 mde week1-week8;
run;
```

where *secondout_wide* is the wide form of the secondary outcome dataset with one observation per participant; *imp1* is the output dataset of monotone missingness; *minimum*, *maximum*, and *round* restrict the imputed values to possible UDS values (negative and positive); *trt* is treatment arm ('rTMS', 'Sham'); *mde* is the major depressive episode (MDE) stratification value, and *week1-week8* provide the UDS values for Week 1 – Week 8, respectively. The analysis method for imputation will follow that used for the secondary outcome analysis. This step provides 50 imputed datasets with monotone missingness by filling in the missing values from intermittent missingness with the statement "impute = monotone." The missing values due to intermittent missingness are imputed assuming that the intervention effect is still carried out while the participants remain in the study.

Using the monotone missingness dataset created in the first step, the second step imputes missing values from dropouts under the assumption of MNAR. This process of control-based pattern imputation assumes that after dropout the unobserved values in the active rTMS arm followed the path of the observed values in the sham arm. Based on this assumption, only the observed values in the sham arm are used to derive the posterior distribution of the parameters from which the missing values in both active rTMS and sham arms are imputed. This approach is conservative as it tended to reduce the difference between active rTMS and sham. The SAS code for imputing missing data from dropout is below.

```
proc mi data = imp1 out = imp2
    minimum = . . . 0 0 0 0
    maximum = . . . 1 1 1 1
    round = . . . 1 1 1 1
```

```
nimpute = 1 seed = 123;
class trt site mde;
var site mde week1 week2 week3 week4 week5 week6 week7 week8;
monotone reg;
mnar model(week1 week2 week3 week4 week5 week6 week7 week8/
modelobs=(trt=Sham));
run;
```

where *site* is the participant's site, *mde* is the major depressive episode (MDE) stratification value, and the remaining variables and proc mi options were as described above. The *monotone reg* statement specifies a regression imputation method for monotone missingness and *mnar* imputed missing values under the MNAR assumption for variables week1-week8. The *modelobs* statement specifies that only observations where *trt* = Sham are used to derive the imputation model following the control-based pattern imputation method.

After the complete datasets are generated, the dataset is transposed into long form by week and analyses of the imputed datasets using the standard procedure for generalized linear mixed effect model are performed separately for each imputed dataset using the *by_imputation_* statement.

```
proc glimmix data = imp_long method = quad;
  by _imputation_;
  class trt (ref = 'Sham') site week mde patid;
  model y(event = '1') = trt mde week site /
    dist = binary link = logit solution;
  random intercept / subject = patid;
  estimate "rTMS vs Sham" trt 1 -1 / cl e ilink exp;
  ods output estimates = est_imp;
run;
```

To draw statistical inference based on the results from the imputations, the combination rules are applied in MIANALYZE procedure (Little and Rubin, 2002; van Buuren, 2007). Proc MIANALYZE is set to estimate the pooled variance from two components: within-imputation variance and between-imputation variance. Within-imputation variance is the average of the mean of the within variance estimate in each imputed dataset. Between-imputation variance reflects the extra variance due to the missing data, which is estimated by taking the variance of parameter of interest estimated over imputed datasets.

```
proc mianalyze data = est_imp;
  modeleffects estimate;
  stderr stderr;
  ods output parameterestimates = est_pooled;
run;
```

The pooled results are then exponentiated to calculate the odds ratio and 95% confidence limits.

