15.6 Missing Data and Dropouts

As defined, the primary (feasibility) outcome will have no missing data. Participants that drop out early will still be evaluated as to whether they attended at least 20 rTMS sessions.

The secondary (efficacy) outcome is expected to have missing data, specifically UDS results. The proposed analysis model takes into account all available data and missing data are assumed to be missing at random (a weaker assumption than missing completely at random). That is, missingness is allowed to depend on observed covariates. As such, the prespecified analysis method does not need missing data to be imputed or handled in some special way. That being said, alternative methods of handling missing data may be considered as sensitivity analyses. Some specific examples may involve imputing a negative UDS in place of missing if that UDS is immediately surrounded by negative UDS, imputing missing UDS results based on self-reported use, or imputing all missing UDS as positive. More technical methods incorporating a missing not at random assumption may also be considered.

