7.10 Updates to Secondary Outcome Analytic Methods

Following database lock, it was determined the planned model-based analyses for the secondary outcome measure could not be completed due to limitations in the data, particularly a lack of variability in the UDS data, estimates at the boundary of the parameter space, and small subgroup sample sizes. This led to highly imprecise estimates which were considered unreliable.

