Table 59: Summary of Negative UDS Results in Participants with rTMS Session Threshold Met¹ by Treatment Arm

Primary Substance of Use	Treatment Arm	Number of Participants with Threshold Met	Results ³				
			Percentage Negative UDS ²	Odds Ratio	95% Lower Confidence Limit	95% Upper Confidence Limit	p-value
Cocaine	Sham	N	n/N (XX.X%)	X.XX	X.XX	X.XX	0.xxx
	rTMS						
Methamphetamine	Sham						
	rTMS						
Overall	Sham						
	rTMS						

¹ Participants met the rTMS session threshold if they completed at least 20 rTMS sessions.

² Outcome is defined as the percentage calculated by the number of negative UDS divided by the number total UDS performed; it includes the last UDS per study week over the 8-week treatment period in the participant's primary substance of use assessed at randomization. Missing UDS are not imputed.

³ Results are obtained from the treatment arm term of the generalized linear mixed model.

Table 60: Summary of Secondary Outcome Sensitivity Analysis by Treatment Arm

Method	Results	N	Odds Ratio	95% Lower Confidence Limit	95% Upper Confidence Limit	p-value
Protocol defined secondary outcome	Secondary outcome (missing UDS not imputed)	N	X.XX	X.XX	X.XX	0.xxx
Sensitivity analysis: Time	Study Week defined as strict 7-day window					
	Time defined using Study Day					
Imputation of missing UDS	Missing UDS imputed as negative					
	Missing UDS imputed as positive					
	Missing UDS imputed based on self-reported use (TLFB)					
	Multiple imputation					

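### Setting missing weekly urine screens to the same value in both arms lets unequal missingness move the odds ratio, and neither resulting row bounds the treatment effect

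*SAP*

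**What the plan says.** The main analysis of the secondary outcome is a mixed logistic model on the observed weekly screens. It imputes nothing; "missing data are assumed to be missing at random" (SAP 7.9).

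SAP 7.9 then lists four alternative ways of handling missing weeks. The first two are "1) imputing all missing secondary outcome measure UDS as negative, and 2) imputing as positive". The third uses self-reported use. The fourth is multiple imputation, with a control-based rule after dropout. A week counts as missing only when it has no screen at all: "if there is not a single UDS collected within the study week, then the secondary outcome is considered missing". Methods 1 and 2 are not restricted by arm or by pattern of missingness, so they also cover all weeks after dropout.

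Protocol 15.6 gave a different list. Its negative-imputation example was limited to "imputing a negative UDS in place of missing if that UDS is immediately surrounded by negative UDS", and its only impute-everything example was "or imputing all missing UDS as positive". The list is introduced as optional ("Some specific examples may involve imputing a negative UDS"). The SAP keeps all-positive, adds all-negative, drops the between-two-negatives rule, and gives no reason.

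The shell for SAP Table 60 gives method 1 its own row, "Missing UDS imputed as negative", with an odds ratio, confidence limits and a p-value.

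**The concern.** Under method 1 each missing week counts as a success. With no treatment effect, the arm that loses more weeks then has more successes and an odds ratio in its favour. Method 2 does the opposite. In either row the odds ratio mixes the treatment effect with the difference in missingness, and the p-value tests the mixture.

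An all-negative row beside an all-positive row also looks like a best case and a worst case. It is not one. The treatment contrast is most extreme when the two arms receive opposite values, and neither method does that. Agreement between the two rows could be taken as robustness that was never tested, and a small p-value in the all-negative row could come from missingness alone.

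**Working it through.** **1. Reproducing the plan's figures.** The documents give no figure for the imputation itself, so the check starts from the plan's power simulation (Protocol 15.2.2, SAP 10.2): 80 participants per use-disorder group, 8 weekly screens, sham probability 0.36, random-intercept SD 1.05 (ICC 0.25) or 1.81 (ICC 0.5), two-sided 0.05. A random-intercept logistic model with the treatment term only, 1,000 runs per cell, gave:

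| Cell | Stated power | Recomputed |
|---|---|---|
| OR 4, ICC 0.5, N=80 | 86% | 85.7% |
| OR 3, ICC 0.5, N=80 | 69% | 68.9% |
| OR 2, ICC 0.5, N=80 | 35% | 33.1% |
| OR 3, ICC 0.25, N=80 | 96% | 96.3% |
| OR 4, ICC 0.5, N=60 | 75% | 74.3% |
| OR 2, ICC 0.25, N=80 | 67% | 64.8% |

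The last cell is 2.2 points off, with a simulation standard error of 1.5 points. The set-up matches the plan well enough to use.

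**2. Arithmetic with no true effect.** Let q be the proportion negative among observed screens, the same in both arms, and m the proportion of missing weeks in an arm.

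- All-negative: proportion negative = m + (1 − m)q
- All-positive: proportion negative = (1 − m)q
- Odds ratio = odds in active ÷ odds in sham

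The documents give no missingness rate by arm. Assume 35% active and 25% sham. Take q = 0.36 from the plan, and q = 0.05 and 0.10 as assumed low-rate cases.

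| q | All-negative, active vs sham | OR | All-positive, active vs sham | OR |
|---|---|---|---|---|
| 0.36 | 0.584 vs 0.520 | 1.30 | 0.234 vs 0.270 | 0.83 |
| 0.10 | 0.415 vs 0.325 | 1.47 | 0.065 vs 0.075 | 0.86 |
| 0.05 | 0.3825 vs 0.2875 | 1.54 | 0.0325 vs 0.0375 | 0.86 |

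For the first cell: 0.35 + 0.65 × 0.36 = 0.584; 0.25 + 0.75 × 0.36 = 0.520; (0.584/0.416) ÷ (0.520/0.480) = 1.30. Equal missingness gives 1.00 in every row. Swapping the arms inverts every odds ratio.

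**3. Effect on the test.** The step 1 model was run with no true effect, N=80, 300 to 400 runs per cell, and missingness unrelated to use within each arm. Missingness was assumed to be 20% sham with 30% or 40% active.

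| q, ICC | Missing, sham/active | All-negative: median OR, false-positive rate | All-positive: median OR, false-positive rate |
|---|---|---|---|
| 0.36, 0.5 | 20%/20% | 0.98, 5.0% | 0.98, 3.8% |
| 0.36, 0.5 | 20%/30% | 1.33, 16.5% | 0.76, 10.5% |
| 0.36, 0.5 | 20%/40% | 1.81, 53% | 0.63, 26.5% |
| 0.10, 0.5 | 20%/30% | 1.46, 36% | 0.81, 7.3% |

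Here 0.36 and 0.10 are the probabilities at a random intercept of zero. Both rows are distorted, in opposite directions.

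**4. What arm-opposed rows would show.** At 30% missing in both arms and q = 0.075, the all-positive proportion is 0.7 × 0.075 = 0.0525 and the all-negative proportion is 0.3 + 0.0525 = 0.3525. Their odds are 0.0554 and 0.5444, so the bounds are about 0.10 and 9.8. At q = 0.36 the proportions are 0.252 and 0.552, and the bounds are about 0.27 and 3.7.

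**5. Reach of the between-two-negatives rule.** At q = 0.075 and 30% missing, with weeks independent, both neighbours of a missing interior week are observed and negative with probability (0.7 × 0.075)² = 0.28%. Six of the eight weeks are interior, so about 0.2% of missing weeks would be filled. With the plan's ICC of 0.5 and the overall rate held at 0.075, the figure is about 0.8%.

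**The case against.** The strongest reply is that the all-negative row should not be judged alone. The same sentence pairs it with all-positive imputation, which penalises the same arm. Table 60 sets both beside the unimputed result, the self-report imputation and a control-based multiple imputation that the SAP calls conservative. SAP Table 46 reports availability of the outcome by week, arm and primary substance, so a reader can see whether missingness differs. The SAP calls these sensitivity analyses, not bounds, and no decision rests on them. All of this stands, and it makes the point a minor one.

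Four stronger readings are tempting, and the documents do not support them.

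- **A breach of the protocol.** Protocol 15.6 offers optional examples, so this is only an unexplained change.
- **A bias towards active treatment.** The direction depends on which arm loses more weeks. More missing weeks on sham would show apparent harm in the all-negative row.
- **Nearly all negatives would be imputed.** That needs a very low observed negative rate. SAP 7.10 reports "particularly a lack of variability in the UDS data" without a rate or a direction. In SAP Table 7, power at OR 2 climbs from 40% to 63% as the sham rate moves by ±0.025, which hints at a low rate but does not state one. At 30% missing, the imputed share of negatives, m/(m + (1 − m)q), is 54% at 0.36 and 81-90% only at 10-5%.
- **The between-two-negatives rule would be the remedy.** By step 5 it would fill under 1% of missing weeks at a low negative rate, and it never reaches weeks after dropout. It would almost repeat the unimputed analysis.

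Nor is an odds ratio in the all-negative row assured: SAP 7.10.2 falls back to a simplified model or to summary statistics when results are unreliable. The same rule could leave that row with an estimate while sparser rows have none, so the pairing is not guaranteed to appear in print.

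**Conclusion.** The point holds as a minor one. Same-value imputation in both arms makes methods 1 and 2 sensitive to any difference in missingness, and together they do not bound the treatment effect. At an assumed 35% vs 25% missing with no true effect, the all-negative odds ratio is about 1.30 at the planned sham rate and 1.47-1.54 at 5-10% negative. The all-positive odds ratio is 0.83-0.86.

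These sizes rest on assumed missingness by arm, assumed low-rate cases, and a marginal calculation; the mixed model's conditional odds ratios differ somewhat (at 20% vs 30% missing and 0.36, arithmetic gives 1.29 and simulation 1.33). With equal missingness the distortion disappears, although the rows still would not be bounds. The departure from the protocol's examples concerns the all-negative row only. The main missing-at-random analysis and the feasibility primary outcome are unaffected.

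**What to change.** - Add two arm-opposed rows to Table 60: missing weeks positive in active and negative in sham, and the reverse. Mark them post hoc, because the database is locked and SAP version 2.0 already follows the lock.
- Keep the all-negative row, since it is prespecified, but label it an extreme scenario not to be read alone. Print missing weeks by arm beside it; Table 46 already supplies the counts.
- State briefly why all-negative replaced the protocol's example. The between-two-negatives rule may be added, but it cannot stand in for a sensitivity analysis of dropout.

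The cost is a few lines of code and two extra rows for each primary substance reported. The real downside is width: if much is missing, the bounds will say little (about 0.10 to 9.8 at 30% missing and 7.5% negative). They would, however, show openly how much the observed data leave undetermined.
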